Intervention software platform. A content management system (CMS) will be the foundation of the software platform that will be developed to support the current study and will provide seamless integration of SMS (text) messaging with the Web-delivered content. As one of the purposes of this research is to be the starting point for wider dissemination of this intervention addressing cancer prevention among this at-risk population, the technology we will implement should also serve as the core for future development. Considering both the characteristics of the target audience as well as the specific requirements of the project, the proposed CMS will 1) allow publication of content in various formats (text, audio, video); 2) asynchronous communication with users using various methods, starting with SMS messaging; 3) synchronous communication with users (e.g., chat); 4) integration with various social media channels (e.g. Facebook); 5) track user interaction with the content and automatically respond to certain user actions (e.g., send SMS reminders if the user does not open the content within a certain period of time), and 6) collect data using automated metrics (e.g., access logs, data usage logs) and survey-like tools. The CMS will be developed by the Health Communication Research core of the University of Kansas Cancer Center, which will also provide know-how and assist with the production of the multimedia content for the Website. In-house development will start from an existing development platform such as Django, Plone, or ModX. This solution uses proven infrastructure to develop a highly customized ecosystem that would be able to combine the above functionality in one integrated software platform and make both problem-solving and future development easy. A dedicated administration page will provide researchers with aggregated as well as individual use, and allow full management of the CMS. User access to content will be PIN-protected, and data transfer will be encrypted. We are leaving nine months to build out the electronic health literacy intervention and six additional months to test it, with additional time if needed.

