Intervention arms and procedures. All women will be mailed a SHE-Women booklet with the intervention content. Electronic women's health literacy intervention procedures (intervention arm). e will deliver the integrated, multimedia electronic women's health literacy intervention arm of SHE-Women in text-Web format for individuals recently released from jail or have recent involvement with the criminal-legal system (2 years). Two health educators will be responsible for delivering content to participants, with an estimated contact time of ~10 hours pushed to participants over approximately a 5-day period. However, because it is a text-Web intervention, accessing content will be dependent on user engagement with the platform. We will measure uptake of the intervention components as it relates to number of minutes of engagement and length of time (total number of days) that all content was accessed. The lead health educator will describe the study and obtain consent from participants. If participants consent, they will immediately be asked to participate in a baseline survey.

For Aim 1 pilot study participants, this will occur over phone or in person in the community. For Aim 2 RCT participants – all of this will occur at the jail at the participant's time of discharge. Participants will be informed that after consent/ after they leave jail, in order to initiate the program, they should contact the health educator through phone, text message, email, or Facebook message. We estimate that we might lose 30% of women between consent and initiation of the community-based intervention, simply because they do not follow-up with us. Thus, in the Aim 1 pilot study we will over-recruit by 15 women; and in the Aim 2 RCT we will over recruit by 60 women, to make up for potential loss to attrition. To improve rates of follow-up, we will also collect multiple points of expected contact information for the participants: phone numbers, addresses for themselves or family members; usual places of hangout; and Facebook handle. That way, if participants don't reach out to us within three days of consent/release from jail, we can contact them.

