Participants who successfully initiate the intervention, over a 5-day period will be sent texts to their mobile phone or messaged through email or Facebook (participant preference) with a link to content on a SHE-Women Website. Content will correspond to Table 2, with tabs for Knowledge, Beliefs, Self-efficacy, Confidence navigating systems, and Wrap-up/review. Content will be delivered through a mix of short videos of the health educators and standardized patient actors discussing content (available in video and audio only format), interactive quizzes, and plain text. Although participants will be able to access content in all five areas, they will receive a daily text message for each area. For example, on Day 1, they will receive a text message to engage in Knowledge content; Day 2, a message to engage in Beliefs content; Day 3, a message to engage in

Self-Efficacy content; Day 4, a message to engage in Confidence navigating health systems content; and on Day 5, a message to complete Wrap-Up content and be invited to complete post-intervention assessments.

A second health educator will monitor whether participants access content after receiving the text messages. If participants have not accessed content within 24 hours of receiving a text message prompt, they will be sent a second text message invitation. If participants still haven't responded, they will receive a phone call from the lead health educator, or a video message through Facebook, that is directly geared toward the participant, re-inviting them to access content for that day.

The SHE-Women Website will also have a tab available to live-chat with a health educator 5 days a week for 8 hours a day. Participants will be able to send messages to the health educator through the SHE-Women Website, if they are not able to live chat. This feature will be available in addition to standard text-message access to a health educator during business hours. We will add weekend or evening hours if necessary.

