Although the text-Web intervention will be designed to be accessed over a continuous 5-day period; participants will be given a three-week window to access all intervention content, to allow for self-directed completion of the text-Web intervention. As soon as participants access all intervention content, the second health educator will be triggered to complete a post-intervention assessment. The post-assessment will be offered to participants over the phone or through an electronic link to the survey.

We will not provide participants equipment or electronic devices. The goal of this project is to assess whether a text-Web intervention is feasible and effective in real life circumstances, thus, with the participants' own devices. We will not pay for any data usage charges to participants. However, because we are compensating participants for study participation, they can use some of the money from study compensation to cover any data usage costs incurred. There are no limitations on what devices can be used. Though participants will have to either receive initial text messages either through a mobile phone or through a private Facebook message. A third option could be through an email address. Participants will then need to be able to access Web content, but they can do that at any place of their choosing: a mobile phone, a home computer, a public library computer, or at some other place.

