Aim 1 pilot and Aim 2 RCT effectiveness outcomes data will be collected in surveys at baseline and post-intervention for Aim 1, and then also at 1, 2, and 3 years for Aim 2. For Aim 1, depending on the method of re-consenting original SHE participants (over the phone or in person), study staff will conduct the baseline assessment either over the phone or in person using a Web link on the SHE-Women study Website. The Web link to the survey will utilize audio computer-assisted self-interview (ACASI) technology, where the computer device will read the questions and answer options aloud as participants move through the assessment. Study staff will make themselves available in person or by phone to guide participants through the Web survey, if they desire this service. Participants will have the option to turn off audio if they cannot gain access to headphones or are in a public place. To facilitate use of ACASI, participants will be offered free headphones at study start, and then at quarterly check-ins, or follow-up surveys. We have used ACASI with other hard to reach low literacy populations with success (active drug users and with women leaving corrections in other cities). For the Aim 2 RCT, study staff will conduct the baseline assessment using the same Web link to the SHE-Women study Website so that participants become accustomed to survey administration using a secure Web link. Participants randomized to the control arm will not have access to any intervention content on the Website. All other surveys – post-intervention, and 1-, 2-, and 3-year follow-up surveys, will be administered using the same Web link to an ACASI-administered survey. Participants will always be given the option of completing the survey over the phone or in person with a member of the study staff, if that is their preference. If participants become re-incarcerated during the longitudinal follow-up, we can conduct surveys in person or through the mail with paper and pencil copies of the survey – we have previously employed these techniques.

Aim 3 perceptions and uptake data will be collected using the same methods described above for Aim 1.

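### Intervention women's immediate post-assessment is assigned to a health educator on the delivery team, with a phone option and no stated separation of delivery from assessment; this could bias self-reported literacy.

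*Combined protocol and SAP*

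**What the plan says.** All references are to the combined protocol and SAP.

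- **Delivery team.** Intervention arms and procedures: "Two health educators will be responsible for delivering content to participants".
- **Second educator's role.** Same section: "A second health educator will monitor whether participants access content after receiving the text messages".
- **Prompting.** If content is not opened within 24 hours, "they will be sent a second text message invitation"; the sender is not named. If there is still no response, "they will receive a phone call from the lead health educator" or a Facebook video message. Under Intervention software platform, the system itself may "send SMS reminders if the user does not open the content within a certain period of time".
- **Intervention-arm post-assessment.** Once all content has been accessed, "the second health educator will be triggered to complete a post-intervention assessment". The next sentence gives the mode: "The post-assessment will be offered to participants over the phone or through an electronic link".
- **Control-arm post-assessment.** The Standard of care discharge planning session paragraph offers the same two modes, phone or link. It says only that the study team will make contact and names no role.
- **General rule.** Data collection says that the post-intervention and annual surveys "will be administered using the same Web link to an ACASI-administered survey". It adds that a woman may always choose to complete by phone or in person with study staff.
- **Outcome type.** Validation strategies states that the primary outcomes, literacy and screening/risk reduction, are self-reported.

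Nothing in the reviewed text describes blinding of assessors or keeps delivery staff out of assessment. Survey mode and assessor are not among the covariates named under Data analysis.

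**The concern.** In the intervention arm, the person assigned the first outcome assessment belongs to the delivery team and has been following that woman's progress. The trigger itself tells the educator the woman's arm and that she has finished the content. If the assessment is a phone interview, she may be reporting her confidence and beliefs to someone linked to the program. The health educators also appear in the program's videos and staff its live chat, and control women cannot reach that Website content.

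The protocol takes educator rapport seriously enough to make its impact the third study goal, so an effect of rapport on reported answers cannot be dismissed. At stake is the immediate post-intervention literacy comparison, one of the two post-baseline time points for literacy in Aim 2. A shift in reporting there would look like a treatment effect, and the planned model has no term to separate the two.

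**Working it through.** **1. Who does what, by arm**

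| | Intervention | Control |
|---|---|---|
| Post-assessment assigned to | Second health educator | Not specified |
| That person's other role | Delivers content, monitors access | Not known |
| Modes offered | Phone or link | Phone or link |
| General rule (Data collection) | ACASI link, staff completion optional | Same |
| Assessor blinding or separation | Not described | Not described |

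The modes match across arms. The asymmetry is in the assessor: a named delivery role in one arm, nobody named in the other.

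**2. The plan's own figure, as a benchmark**

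Inputs from the Power section: N=124, t=3 for literacy, r=0.46, alpha 0.05, and f printed as both 0.12 and 0.13. For a two-group within-between interaction:

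λ = f²·N·t/(1−r), with df1 = t−1 = 2 and df2 = (N−2)(t−1) = 244.

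- f=0.12: λ = 0.0144 × 124 × 3 / 0.54 = 9.92, power 80.7%. This reproduces the stated 80%.
- f=0.13: λ = 0.0169 × 124 × 3 / 0.54 = 11.64, power 86.9%. This does not.

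So f=0.12 is used below.

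**3. f=0.12 in SD units**

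- Two visits: f = d/4, so d = 4 × 0.12 = 0.48 SD.
- Three visits, with the difference at the post visit only: the interaction residuals are ∓b/6, ±b/3, ∓b/6. Their mean square is b²/18, so f = b/√18 and b = 0.12 × 4.243 = 0.51 SD.

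**4. Illustration of a reporting shift (assumed, not from the documents)**

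Let b be the net arm-average shift at the immediate post visit: the share of intervention women assessed by phone or with staff times the shift per interview, minus the same product in the control arm. With no true effect and no shift at the other visits, λ = (b²/18)·N·3/0.54. That is 38.27·b² at N=124 and 61.73·b² at N=200. At N=200, df2 = 198 × 2 = 396.

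| Net shift b (SD) | Share of 0.51 SD | False-positive rate, N=124 | N=200 |
|---|---|---|---|
| 0.05 | 10% | 5.7% | 6.2% |
| 0.10 | 20% | 8.0% | 9.9% |
| 0.20 | 39% | 17.9% | 26.9% |
| 0.30 | 59% | 36.0% | 54.6% |

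**5. The share exposed drives the answer**

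Take an assumed shift of 0.20 SD per interview and none in the control arm. If 25% of intervention women are interviewed, b = 0.05; if 50%, b = 0.10; if all, b = 0.20. If the same educator interviews control women in the same proportion and with the same effect, b = 0. The documents do not say which case applies.

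**The case against.** The strongest reply is that the protocol already makes ACASI the standard mode in both arms, so only women who choose phone or staff completion are exposed. Both arms have the same modes, and the unnamed control assessor may be the same educator. Women in both arms also have contact with educators: the lead educator takes consent, and all participants receive the study phone number and session invitations. Most of this stands. It limits the size of any bias, but it does not supply the missing separation of roles. Monitoring and the program videos still belong to one arm only.

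Several stronger readings are tempting and are not supported:

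- **That the assessor is also the person who prompts the women.** The second educator is said only to monitor. The repeat text has no named sender and may be automated, and the call is the lead educator's.
- **That the sections contradict each other on mode.** Data collection expressly allows phone or in-person completion, so they agree.
- **That the educator necessarily interviews.** Being triggered to complete the assessment may mean only sending or arranging the link, since a link is offered in the next sentence.
- **That bias is established and runs through the whole arm.** Applying 0.1-0.2 SD to every intervention woman, about 20-40% of the planning effect, ignores that only interviewed women are exposed.
- **That all literacy items are equally vulnerable.** Knowledge items with correct answers are probably less so; this is a judgement.

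The arm-specific assignment also concerns the immediate post-assessment only, not the 1-year literacy survey.

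**Conclusion.** The concern holds as a risk, not as a demonstrated bias. A delivery-team educator who knows the woman's arm and has monitored her engagement is assigned her first outcome assessment, with a phone option. The control assessor is unspecified, and the reviewed text describes no safeguard. Because the outcome is self-reported, this could favor the intervention at the immediate post-intervention visit among women who complete by phone or with staff.

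The size cannot be estimated from the documents. The illustrative false-positive rates (about 6-18% at N=124 for net shifts of 0.05-0.20 SD) rest on assumed shifts, equal correlation of 0.46 between visits, no true effect, and a shift at one visit only. The true figure could be close to the nominal 5% if few women are interviewed or if both arms are interviewed alike. The plan should be changed because the weakness is avoidable at little cost; the sample size is not affected.

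**What to change.** 1. In the intervention-arm and control-arm procedures, state that the self-administered ACASI link is offered first for the post-assessment in both arms. Limit the educator's role to sending the link, and reword the trigger sentence accordingly.
2. Keep the phone and in-person options. In both arms, under one rule, assign them to existing study staff who did not deliver or monitor content for that woman. The document mentions study staff under Data collection and a research associate under Data analysis. It gives no staffing roster, so the sponsor should confirm who is free of delivery duties.
3. Record mode and assessor role for every survey.
4. Report literacy results by mode as a labelled sensitivity check only. Mode is chosen after randomization, so an ACASI-only comparison is not a randomized one and can introduce selection of its own.

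If post-assessments have already been done, recover mode and assessor where possible and report them by arm. The cost is some reassignment of existing staff tasks and one or two data fields.

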Aim 2 RCT settings will be various locations in the Kansas City metro: two urban city/county jails in Kansas City – one facility on the Missouri side of the state line, and one facility in Kansas. We will also recruit women in various community settings with the women having a release date of five years post incarceration. We will recruit women in social support centers, DV shelters, transitional living facilities and other community organizations where our population may frequent. Our goal is to work with women leaving jail or with recent criminal justice involvement using an electronic women's health literacy intervention modality; volunteer for the study; and do not exhibit psychological distress, which would prohibit informed consent. There are no age or medical study exclusions, since all women could potentially benefit for guidance on cervical, breast, unintended pregnancy, and STI screening. For recruitment in jails, we will work with discharge planners to recruit women scheduled to be released from jail. The jail staff will distribute hygiene packets to women as they are being released while introducing the program. Included in these packets, the women will see a business card with our picture and contact info so that if they are interested, they can call us. For sampling, on any given day, about 120 women are incarcerated in the KC, MO facility and 45 women are incarcerated in the KC, KS facility. In local community organizations, we will distribute our 'flyer' that will be placed in the organization, where the population frequents. We will recruit a convenience sample of N~260 women for the RCT, oversampling to account for attrition, with the goal of ending with N~200 women for the RCT. In our previous studies, we have found that in these facilities between 1-4 women are released each day, and that we were

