Standard of care discharge planning session (control arm). In the Aim 1 pilot study, participants will only access the intervention arm content. In the Aim 2 RCT, participants will be randomized after consent to the intervention or control arm. The women will be offered a 10-page women's health booklet that utilizes SHE-Women content, but in print form. The booklet will provide simple definitions, screening guidelines, and local health resources for age and risk appropriate cervical, breast cancer, unintended pregnancy, and STI prevention. We will collect multiple points of contact information for the participants: phone numbers, addresses for themselves or family members; usual places of hangout; and Facebook handle, for follow-up. Participants in this arm of the intervention will be contacted 5 days after receiving the standard of care intervention for post-assessment. Similar to the intervention arm, we expect to lose 30% of women to follow-up, thus we will over-recruit by about 30% for the RCT, as described above. Participants will be asked to reach out to us 5 days after or we will contact them for follow-up and to complete the post-assessment over the phone or through an electronic link to the survey.

We wish to note that although we call the control arm the "standard of care," in reality there is no standard discharge planning session in the jails we work with; women are sent out the door with their belongings. But we feel it would be grossly unethical to not provide the control arm with some health information, even if limited.

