Power. The sample size for the Aim 1 feasibility study is based on our original SHE study pilot and expanded to allow for rigorous testing and refining of modality.²⁶ The sample size of N~200 for the Aim 2 RCT was determined to provide satisfactory power ($\geq 80\%$) for this study in addressing the specific aims, which depends on the following parameters: number of participants (n), number of measurements (t=3 for health literacy for screening; t=4 for screening/risk reduction practices), effect size (f) as group difference in change, correlation between repeated measures (r), and attrition rate. The effect sizes estimated from the original SHE study were in the small to moderate range—for health literacy (8 domains), average $f=0.13$ at immediately post-intervention and 0.16 at 1-year post-intervention; $f=0.17$ for cervix screening and 0.12 for condom use during the last intercourse at 1-year post-intervention. Although effect sizes for breast cancer screening and STI screening are not available from the original SHE study, we expect similar, small to moderate effect sizes for these outcomes. Thus, we conservatively assumed the smallest observed effect size of $f=0.12$ for our power calculation. The correlations between repeated measures observed in the original SHE study were $r=0.46$ on average, with the range of 0.39-0.75 between baseline and immediately post-intervention and 0.25-0.61 between baseline and 1-year post-intervention. Power analysis of these data ($f=0.13$, $t=3$ or 4, $r=0.46$) and G*Power 3.1.9.2 indicated that a sample of 124 women will produce $\geq 80\%$ power for both health literacy (80%) and screening/risk reduction behaviors (85%). In our original SHE study, the 3-year follow-up rate was 85%. Conservatively assuming a high attrition rate up to 40%, we will recruit ~200 women at baseline to adequately power the SHE-Women study—i.e., maintain $\geq 80\%$ power even with a low follow-up rate as small as 60%. As

Table 4. Expected attrition over study period

	Aim 1 feasibility Target N~20	Aim 2 RCT Target N~200	Aim 3 (same as Aim 2)
Consent and baseline	20	260	--
Intervention initiation	15	220	--
Post-intervention	10	200	--
1 year follow-up	--	170	--
2-year follow-up	--	160	--
3-year follow-up	--	150	--

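### The 60 over-recruits do not cover the 30% loss the plan expects, the attrition figures disagree, and power makes no allowance for women who never start

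*Combined protocol and SAP*

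**What the plan says.** For RCT women, *Intervention arms and procedures* places consent and the baseline survey at the jail at discharge. After release, "in order to initiate the program, they should contact the health educator through phone, text message, email, or Facebook message". The control-arm section says "In the Aim 2 RCT, participants will be randomized after consent to the intervention or control arm" and names no later time.

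The expected loss and its cover appear in four places:

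- *Intervention arms and procedures*: "We estimate that we might lose 30% of women between consent and initiation of the community-based intervention", and "in the Aim 2 RCT we will over recruit by 60 women, to make up for potential loss to attrition".
- *Standard of care discharge planning session (control arm)*, which describes the loss as similar to that in the intervention arm: "we expect to lose 30% of women to follow-up, thus we will over-recruit by about 30% for the RCT".
- *Settings, eligibility, recruitment, and sampling*: about 260 women are recruited, "oversampling to account for attrition, with the goal of ending with N~200 women for the RCT".
- Table 4, Aim 2 column: 260 at consent and baseline, 220 at initiation (the row reads "Intervention initiation 15 220", Aim 1 then Aim 2), 200 at post-intervention, then 170, 160 and 150 at years 1 to 3.

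The *Power* section asks for 124 women and allows for up to 40% attrition from about 200 at baseline. It takes its effect sizes from the original SHE study and commits to an intention-to-treat analysis with multiple imputation.

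**The concern.** Two things are at stake. First, the plan states an expected loss, a recruitment number and a final number that do not fit together, so a reader cannot tell how many women the trial expects to have or at what stage. The 30% is a loss before initiation in one section and a loss to follow-up in the next, Table 4 uses neither, and 200 is a baseline count in one place and a post-intervention count in another.

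Second, women who are randomised and never start belong in the intention-to-treat comparison. Keeping them is right, but it lowers the average effect. The power calculation allows for lost numbers and not for a smaller effect. Its source may not contain that reduction either: *Progress report for this study* describes the earlier literacy gains among 182 women who completed, out of 261 who consented.

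**Working it through.** **Recruitment number.** Inputs: target 200, loss 30%, over-recruitment 60.

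- The plan's figure: 200 × 1.30 = 260. This reproduces it exactly.
- What 260 leaves at a 30% loss: 260 × 0.70 = 182, which is 18 short of 200.
- The loss that 60 extra women cover: 60/260 = 23.1%.
- Consents needed to end with 200: 200/0.70 = 285.7, so 286.
- Table 4: 1 − 220/260 = 15.4% by initiation; 1 − 200/260 = 23.1% by post-intervention.
- If 30% is lost by initiation and Table 4's later drop (220 to 200) still follows: 182 × 200/220 = about 165 at post-intervention.

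**Power, undiluted.** I used the repeated-measures group-by-time interaction with two groups: λ = f²·N·t/(1 − r), df1 = t − 1, df2 = (N − 2)(t − 1), alpha 0.05, r = 0.46, with t = 3 for literacy and t = 4 for screening and risk reduction.

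The *Power* section says it assumes f = 0.12 and then prints f = 0.13. At N = 124 and f = 0.12, t = 3 gives λ = 0.0144 × 124 × 3/0.54 = 9.92 and power 80.7%, matching the stated 80%. For t = 4 the result is 87.3%, against the stated 85%. At f = 0.13 the results are 86.9% and 92.4%, which match neither figure. I therefore use 0.12 and give 0.13 as a sensitivity check.

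At N = 182 and f = 0.12, power is 93.5% (t = 3) and 97.0% (t = 4). Carrying 182 from initiation to year 3 at Table 4's rates gives 182 × 150/220 = 124, the number the plan says it needs.

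**Power, allowing for non-initiation.** Assumption: intervention women who never start gain nothing, so f is multiplied by the share who start. At 30% non-start, f = 0.12 × 0.70 = 0.084. At Table 4's rate, f = 0.12 × 220/260 = about 0.102. N is the number of women who effectively contribute outcome data.

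| Non-start | N | t = 3 | t = 4 |
|---|---|---|---|
| 30% | 182 | 66% | 73% |
| 30% | 200 | 70% | 78% |
| 30% | 260 | 82% | 89% |
| 15.4% | 150 | 75% | 82% |
| 15.4% | 200 | 86% | 92% |

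For example, 30% non-start with N = 200 and t = 3 gives λ = 0.084² × 200 × 3/0.54 = 7.84. Starting from f = 0.13, 30% non-start gives 78%/85% at N = 200 and 73%/81% at N = 182.

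**The case against.** The strongest reply is that little depends on 200. The calculation needs 124 women, 182 undiluted gives well over 80%, the 30% is worded as a possibility, and staff will contact women who have not been in touch within three days. *Strategies for success* says more women can be recruited if attrition is high, and Table 4's own rates reach exactly 200. All of that stands against any claim that the shortfall by itself breaks the stated power. It does not make the three sets of figures agree, and it does not address the smaller effect. The 40% attrition allowance changes N and leaves f untouched. Imputation cannot restore an effect that non-starters did not have.

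The 30% may also not apply to everyone. Women who respond to a business card or flyer, or who are referred by a friend, contact the team before they consent. That is fair, and is a reason to state the rate by recruitment route.

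A reader might infer three stronger points, which the documents do not support:

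- *That randomisation is wrongly placed and must move to a post-release contact.* The text says after consent and gives no time, so its place before that contact is an inference, though a natural one. Keeping non-starters is correct under intention to treat. The plan also says it wants effectiveness in real-life conditions, where failure to start is part of the effect. Randomising only women who make contact estimates the effect in a different population. Any gain in information from doing so depends on zero effect in non-starters and on outcome data from all 260, and is not established.
- *That loss will differ by arm.* Only intervention women have an initiation step, but the plan expects similar loss in controls and Table 4 is not split by arm.
- *That randomised women will be dropped to leave 200.* The intention-to-treat commitment says otherwise; the wording about ending with 200 only leaves the point unclear.

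**Conclusion.** The inflation is miscalculated. At the plan's own 30%, 260 consents leave about 182, and 200 would need about 286. The 30% also conflicts with Table 4's 15.4% and 23.1%, and the 200 is placed at two different stages. These findings follow from the plan's figures alone.

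The effect on power is conditional. The shortfall alone leaves power above 80%. With 30% non-start, no effect in non-starters and f = 0.12, power is about 70%/78% with 200 women and 66%/73% with 182, below the stated 80% or more. It returns to 82%/89% only if all 260 contribute outcomes. At Table 4's 15.4% it holds at 200 women, but falls to 75% for t = 3 at 150, Table 4's year-3 number; literacy, the t = 3 outcome, is due only to year 1. Some benefit in non-starters, or a true effect nearer 0.13, would soften this. That the source effect sizes are undiluted is itself an inference: the plan reports the literacy gains among completers and does not state the analysis set behind the screening and condom-use figures.

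**What to change.** - Use one attrition rate, tied to a named stage, in the intervention-arm section, the control-arm section and Table 4. If 30% is kept, state about 182 from 260, or plan about 286 consents. If 200 from 260 is kept, state a loss of about 23%.
- Say whether 200 is the number at baseline or at post-intervention, and make the *Power* section and Table 4 agree.
- State when randomisation takes place for each recruitment route, and that every randomised woman, including those who never initiate, is in the intention-to-treat set.
- Restate power with an explicit allowance for non-initiation over a range that includes 15.4% and 30%, using a single value of f.

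The cost is wording and a short recalculation. Only a decision to hold 200 at a 30% loss adds recruits: 286 − 260 = 26 more consents. If the sponsor prefers to randomise at a post-release contact, that is an optional design choice. It should be justified as a change in the population estimated and reconciled with the control arm's discharge session.
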